### **1.2 Secondary:**

- 1- To compare post-transplant recovery of innate and adaptive immune cells (CD8, CD4, CD19, NK,  $\gamma\delta$  T-cells), in addition to T-cell phenotype markers between the two arms.
- 2- To compare post-transplant recovery of T-reg and MDSCs between the two arms.
- 3- To compare progression free survival (PFS) at 2 years post-transplant

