### **5.4 Duration of the study.**

The study is expected to last approximately 24 months.

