## Section 7.0 Study Parameters

Examinations and Assessments	Baseline (Screening)	Pre-Transplant (SCT)				Transplant	Post Transplant Period										Follow up Period
	Pre vaccine	Vaccine (day -19)	Day -12 to -9	Day -11 to -7	Day -6 to -4	AHSCT Hospitalization	Day + 7	Day +15	Day +30	Day +60	Day +70	Day +100 (mo. 3)	Day +130 (mo. 4)	Day +150 (mo. 5)	Day +180 (mo. 6)	Day +365 (1 yr)	Survival status (2 years)
Window Days for Study Visit 	-30 days (+/-10 days)					Day 0		+/-3	+14	+/-3	+14	+/-10	+/-7	+/-7	+/-10	+/-30	+/-30 days
Informed Consent	X																
Inclusion/Exclusion Criteria	X																
Pregnancy testing	X 																
Medical History	X																
Clinical Assessment	X 																
Data collection to assess organ function (labs) 	X																
Disease response 	X												X			X	X
Data collection for Disease Assessment													X				

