## Section 7.0 Study Parameters

Examinations and Assessments	Baseline (Screening)	Pre-Transplant (SCT)				Transplant	Post Transplant Period										Follow up Period
	Pre vaccine	Vaccine (day -19)	Day -12 to -9	Day -11 to -7	Day -6 to -4	AHSCT Hospitalization	Day + 7	Day +15	Day +30	Day +60	Day +70	Day +100 (mo. 3)	Day +130 (mo. 4)	Day +150 (mo. 5)	Day +180 (mo. 6)	Day +365 (1 yr)	Survival status (2 years)
(imaging and bone marrow)																	
Data collection for Disease assessment (blood and urine)	X											X			X	X	X
Adverse Events						X	X	X	X	X	X	X	X	X	X	X	X
Assessment for Subject/Graft Survival							X	X		X	X			X			X
Hematology (complete blood count (CBC) with differential ALC platelets)	X					X	X	X	X	X	X			X	X	X	
Randomization	X																

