## Section 7.0 Study Parameters

Examinations and Assessments	Baseline (Screening)	Pre-Transplant (SCT)				Transplant	Post Transplant Period										Follow up Period
	Pre vaccine	Vaccine (day -19)	Day -12 to -9	Day -11 to -7	Day -6 to -4	AHSCT Hospitalization	Day + 7	Day +15	Day +30	Day +60	Day +70	Day +100 (mo. 3)	Day +130 (mo. 4)	Day +150 (mo. 5)	Day +180 (mo. 6)	Day +365 (1 yr)	Survival status (2 years)
Tetanus Vaccine		X						X		X							
Group 1  / Pre G-CSF PBMC pheresis			X														
Group 1 – Post-AHSCT PBMC infusion							X										
G-CSF (both groups)				X													
Pre Stem Cell harvest / Graft Pheresis (both groups) 					X												
Immune correlative study blood draw		X	X 		X			X	X		X	X		X			

 Pre-PBMC harvest in group 1 7-10 day post vaccine only

Clinical Assessment is billed as physical exam with performance score. Data will be collected for MM disease specifics. Height and weight are also collected only at screening.

 Disease response to be done at discretion of physician in keeping with standard of care.

 Transplant day is day 0.

 Female of child-bearing potential must have two negative urine pregnancy test results within at time of eligibility testing and prior to GCS-F pre-transplant as a way of ensuring safe transplant planning.

Organ function measured by standard clinical care labs collected from CBC, complete metabolic panel to assess the kidney, liver function.

 Subjects will receive one dose of plerixafor, a stem cell mobilizer, followed by pheresis on the next day to collect G-PBSC graft

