### **10.2 Secondary Objectives**

For the secondary objectives, engraftment, development of any auto immune side effects, and infections will be treated as binary variables. Chi-square tests will be used to compare each of these 3 outcome variables between the two groups, respectively. A Wilcoxon signed-ranks test will be employed to test the change in absolute lymphocyte (ALC), absolute monocyte counts (AMC), immune cells (T cells CD8, CD4), natural killer cells,  $\gamma\delta$  T-cells, T-reg and MDSCs) at days 15 and 30 post AHSCT from the baseline among each group, respectively. Wilcoxon signed-ranks test will be further used to compare the change of change in ALC, AMC and immune cells between the two groups at days 15 and 30 post- AHSCT, respectively.

Generalized linear mixed models will be employed to compare the change pattern of ALC, AMC and immune cells between the two groups over the entire follow up periods. Time to relapse and overall survival will plotted using the methods of Kaplan and Meier and the log rank test will be used to compare the time to event curves between the two treatment groups.

Lastly, as an explorative objective will also be depth of anti-myeloma response as evaluated by the standard IMWG criteria, including the rate of sCR, and subsequent MRD status for the subjects in sCR.

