#### **Section 14.0 Data Collection Forms:**

A data collection plan for electronic data capture forms (eCRF) is submitted as part of this protocol for the scientific review committees review. This plan includes data capture forms for the following:

- Adverse Event Log
- Clinical Laboratory Values
- Death Record
- Eligibility Checklist (including both inclusion and exclusion criteria to match the protocol)
- Medical History
- Physical Examination

In addition, the study team has the following items provided, at the time of site activation, as an accompaniment to the protocol. These items are provided electronically as a study site manual and Manual of Operations (MOP) to guide the study operations. Below are the included forms.

- Manual of Operations document
- Study site manual
  - Delegation log template
  - Training log template
  - Enrollment/Registration documents – registration request, eligibility exception request and ineligibility report and enrollment log
  - Td Vaccine Information sheet for subjects
  - Investigator's brochure, package insert
  - DSMC/ Federal AE/SAE reporting documents
  - Specimen collection and prep worksheet – Lab Manual
  - eCRF completion guidelines
  - FDA 1572, FDA 3455 Financial disclosure, as appropriate

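### The secondary objective is 2-year progression-free survival, but Section 10.2 analyses only an undefined time to relapse and overall survival

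*Combined protocol and SAP*

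**What the plan says.** Section 1.2 lists as its third secondary objective "To compare progression free survival (PFS) at 2 years post-transplant", in the setting of a comparison of the two arms.

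Section 10.2 is the only place where secondary analyses are planned. Its time-to-event sentence reads "Time to relapse and overall survival will plotted using the methods of Kaplan and Meier and the log rank test will be used", with the groups set against each other. PFS is not mentioned there. Overall survival is analysed, but none of the objectives in Sections 1.1 to 1.3 names it.

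Elsewhere PFS appears only in the background of Section 2 and in reference titles. No section gives PFS or time to relapse a starting point, an event definition, a rule for death without relapse, or a censoring rule. The International Myeloma Working Group (IMWG) criteria are used for diagnosis and for depth of response, but not to define a progression or relapse event.

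The schedule in Section 7.0 runs to a final column headed "Survival status (2 years". As I read the table, the disease response row and the row "Data collection for Disease assessment (blood and urine" are both marked at that visit. A footnote to the disease response row says "Disease response to be done at discretion of physician in keeping with standard of care".

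**The concern.** The objective and the analysis name different endpoints. By usual convention PFS counts death from any cause as an event. Time to relapse usually censors such a death or treats it as a competing event, and here the protocol does not say which. An analyst who follows Section 10.2 to the letter produces no PFS result and no 2-year figure. An analyst who wants to answer the objective must choose the origin, events, censoring and 2-year reading after the data exist. A log-rank test of whole curves is also not in itself a comparison at 2 years.

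Death without relapse could matter to this comparison. Section 2.5 reports more viral and bacterial infections after CD34-selected autologous transplant than after standard transplant, and CD34 selection is part of the experimental arm. Section 5.3 names engraftment failure, autoimmunity and severe lymphopenia as possible complications in group 1. If such deaths are censored, treatment-related mortality disappears from the disease-control curve. Against this, Section 5.3 expects the day +7 lymphocyte infusion to make lymphopenia unlikely, and the documents do not say how often such deaths occur.

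**Working it through.** The finding is one of consistency. The documents give no figure for PFS, time to relapse or overall survival, so there is none to reproduce. The arithmetic below only shows scale.

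**1. Objective against analysis**

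| Item | Section 1.2, objective 3 | Section 10.2 |
|---|---|---|
| Endpoint | PFS | Time to relapse; overall survival |
| Time point | 2 years | None (whole curves) |
| Death without relapse | Not stated | Not stated for time to relapse |
| Origin and censoring | Not stated | Not stated |

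Section 2.6 uses relapse, PFS and overall survival as separate terms, so the protocol does not itself treat them as synonyms.

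**2. How far the endpoints can part**

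Input from Section 5.5: 10 subjects per arm. Assumed for illustration: three relapses and one death without relapse within 2 years, and no other censoring.

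- PFS at 2 years: (10 − 3 − 1)/10 = 6/10 = 60.0%.
- Relapse-free by Kaplan-Meier, death censored before all three relapses: (8/9)(7/8)(6/7) = 6/9 = 66.7%.
- Relapse-free by Kaplan-Meier, death censored after all three relapses: (9/10)(8/9)(7/8) = 7/10 = 70.0%.
- Gap: 66.7 − 60.0 = 6.7 points, up to 70.0 − 60.0 = 10.0 points.

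With no death without relapse, and if relapse is taken to mean progression, both estimates are 7/10 = 70.0% and the gap is zero.

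**3. Precision at 10 per arm**

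With complete follow-up S = k/10. The 95% interval on the log(−log) scale is S^exp(±1.96·se), with se = √[(1 − S)/(10S)] / |ln S|.

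- 6/10: se = √(0.4/6)/0.511 = 0.506; interval 25–83%.
- 7/10: se = √(0.3/7)/0.357 = 0.580; interval 33–89%.
- 8/10: se = √(0.2/8)/0.223 = 0.709; interval 41–95%.

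**4. Power of a log-rank comparison**

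Assumed: exponential times, hazard ratio 0.5, all subjects followed for 24 months, two-sided 5%, control 2-year PFS p of 60%, 70% or 80%. Expected events are 10(1 − p) + 10(1 − √p) = 6.3, 4.6 and 3.1. Simulated power (20,000 runs each) is about 13%, 10% and 5%. A test on so few events cannot confirm or rule out a benefit.

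**The case against.** The best case on the other side is that this is a loose label in a 20-subject pilot. Time to relapse is undefined, so nothing proves that the authors meant to censor deaths. PFS can be derived from relapse and death dates. The endpoint is secondary, and with power of roughly 5–13% under the assumptions above no usable test results under either name.

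Much of this stands as to weight. It supports a short wording correction and a descriptive label. It does not remove the mismatch: an undefined endpoint under another name does not answer a stated objective, and deriving PFS later means setting its rules after the data are seen.

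A reader might infer more than the documents support:

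- **That the data for 2-year PFS will not be collected.** Disease response, blood and urine disease data, and survival status are all marked at 2 years. The footnote leaves disease response to the physician, but the visit is planned. The list in Section 14.0 names no progression form, yet it also names none for the ELISPOT, ELISA or flow assays that serve the primary and secondary objectives. Its silence shows nothing.
- **That the trial is too short for a 2-year endpoint.** Section 5.4 says "The study is expected to last approximately 24 months", which fits if it is a duration per subject. The section does not say which duration it means, and the question is separate from the choice of endpoint.
- **That the two endpoints must give different results.** They do so only if someone dies without relapse.

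**Conclusion.** The point holds as a mismatch between objective and analysis. Section 1.2 sets a comparison of 2-year PFS, Section 10.2 analyses two other endpoints, and no section defines PFS or plans a 2-year estimate. The reading of the text is certain and depends on no calculation.

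The numerical effect is conditional. It is zero if nobody dies without relapse and relapse means progression. It is 6.7 to 10 percentage points in the illustrative arm with one such death and three relapses. That illustration assumes complete follow-up otherwise and the usual practice of censoring deaths in time to relapse. The documents do not allow a forecast of how many such deaths there will be.

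The change should be made, because it is specific and cheap. It does not touch the primary vaccine-response analysis.

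**What to change.** In Section 10.2, name PFS as the analysis for the third objective of Section 1.2 and specify:

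- **Definition:** from transplant day 0 to first progression by IMWG criteria, which the protocol already uses for response, or death from any cause. Progression before day +100 counts as an event. Other subjects are censored at the last disease assessment.
- **Population:** by randomised arm, including subjects moved to group 2 after missing the CD34 minimum. The separate analysis of those subjects in Section 5.1.6 can be kept as an addition. Subjects randomised but never transplanted have no day 0 and are reported separately.
- **Reporting:** Kaplan-Meier curves, and the 2-year estimate with its 95% confidence interval and number at risk per arm. Label the comparison descriptive at 10 per arm.
- **Other endpoints:** define time to relapse and keep it and overall survival as additional analyses, or drop them.

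The cost is protocol wording. No new visits are needed, because the disease and survival assessments at 2 years are already in Section 7.0. The drawback is that the PFS comparison stays imprecise; better wording cannot change that with 20 subjects.

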### **10.3 Study Design:**

This is a pilot phase II trial with 1:1 randomization between the experimental and control arms.

### **10.4 Stopping Rules**

If more than three subjects on the experimental arm develop a treatment related grade 3-4 toxicity, which is irreversible, protocol will be halted and the Institutional Review Board will be notified.

### **10.5 Sample Size and Power Consideration**

This is exploratory trial with a total sample size of 20 subjects total (10 subjects in each phase II arm). There is no preliminary data on the primary endpoint of the study (baseline tetanus vaccine response early after transplant). However, it is known that vaccine response in general is muted in the first three months post-transplant. We hypothesize to see a wide difference in Elispot values between the two arms. Two-sided two sample t-test is used to for power calculation. The sample size of 20 will achieve a power of at least 80% to detect an effect size of  $d=1.36$  for a Mann-Whitney test comparing two independent groups at the significance level of 5% assuming that the actual distribution is Normal. Because of the exploratory nature of the study, corrections for multiple comparisons will not be performed. Significance for each test will be set at  $P<.05$ .

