#### 5.1.6 Graft processing on the experimental arm

The stem cell product may start to be washed while waiting for the CD34+ content to known. Subjects who fail to mobilize a minimum of 6 million CD34/kg on day 1 of leukapheresis will be removed from the experimental arm of the study (these subjects will be treated and followed like group 2 for a separate analysis at the end).

- Subjects who mobilize 6-10 million CD34/kg on day 1:
  - will proceed to CD34 stem cell selection on the Milteny device, provided that the TNC content does not exceed the column capacity. They will proceed to day 2 collection to complete CD34 need for second stem cell transplant 2 million CD34/kg + 2 million CD34/kg reserve for potential “boost” need in case of graft failure on protocol (hence 4 total).
- Subjects who mobilize >10 million CD34/kg on day 1:
  - They can have approximately up to 10 million CD 34/kg processed on the Miltenyi column, if the TNC content does not exceed the column capacity (remainder difference for the second AHSCT and the boost will be collected on the following day 2 of collection).
- Collecting at least 14 million CD34/kg on day 1 will complete stem cell collection process(10 for Miltenyi, 2 for second AHSCT and 2 for boost).

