### **5.6 Removal from the study**

Subjects who for whatever reason do not meet the cardiac ejection fraction, pulmonary function test requirement or develop significant organ dysfunction before the transplant admission will be removed from the study.

The investigator will withdraw a subject from the study treatment whenever:

1. Continued participation is no longer in the subject's best interests. Reasons for discontinuing treatment may include the occurrence of a SAE or an inter-current illness. These subjects will be taken off treatment and followed according to the study calendar.
2. The subject requests to end treatment.
3. Subjects who fail to collect a minimum of 6 million CD 34 cells/kg body weight at the end of 1st day of Leukapheresis will be either removed or transferred to arm 2 of the protocol after discussion with the PI.

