## **Section 10.0 Statistical Considerations:**

### **10.1 Primary Objectives**

Given the known lack of vaccine response in the first few months post autologous stem cell transplantation, we intend to look for evidence of vaccine response in the experimental arm via increase in tetanus specific T-cell Elispots and anti-tetanus antibody (Elisa) on days 30, 70, 100 and 180 post-transplant. Given the pilot/explorative nature of this trial and the lack of good pre trial assumptions about vaccine response, we will evaluate the vaccine response by Elisa and Elispot on days 30, 70, 100 and 180 will be compared between groups using a Mann-Whitney test.

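### The power of at least 80% at d = 1.36 holds only under a large-sample approximation with all 20 subjects analysed; a Mann-Whitney test that keeps the 5% level has about 78%, and less after any removal

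*Combined protocol and SAP*

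**What the plan says.** Section 10.5 fixes the size of the trial: "This is exploratory trial with a total sample size of 20 subjects total (10 subjects in each phase II arm"). It gives the basis of the calculation, "Two-sided two sample t-test is used to for power calculation", and then the result: "The sample size of 20 will achieve a power of at least 80% to detect an effect size of" d = 1.36 for a Mann-Whitney test, "at the significance level of 5% assuming that the actual distribution is Normal". It applies no correction for multiple comparisons.

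Section 10.1 names the same test for the primary analysis: ELISA and ELISPOT responses "on days 30, 70, 100 and 180 will be compared between groups using a Mann-Whitney test". It does not say whether the test is exact, continuity-corrected or uncorrected.

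Section 5.5 lets up to 29 subjects be screened, to cover screen failures. No allowance is made for losses after randomisation, and replacement of randomised subjects is not mentioned. The calendar in Section 7.0 places randomisation at baseline, before mobilisation. After that point:

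- Section 5.1.6: "Subjects who fail to mobilize a minimum of 6 million CD34/kg on day 1 of leukapheresis will be removed from the experimental arm", with a separate analysis of them at the end.
- Section 5.6: the same subjects "will be either removed or transferred to arm 2 of the protocol after discussion with the PI".
- Section 5.2.2: progression before day 100 takes a subject off study.
- Section 8.2: vaccine toxicity of grade 3 or more after the first vaccination takes a subject off trial.

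**The concern.** The power sentence gives a lower bound for a named test at a named level. With 10 per arm the Mann-Whitney statistic takes few values near its critical point, so the attainable significance level can sit well below 5% and power falls with it. A large-sample calculation does not see this. The sentence also needs every randomised subject to be in the comparison, while the plan's own rules can take some out, most directly from the experimental arm.

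The stake is how a null result is read. The stated bound implies a chance of at most 20% of missing a true difference of 1.36 SD in one comparison. If the real chance is nearer 22% with everyone analysed, and more after losses, the report should say so.

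**Working it through.** **Inputs.** 10 per arm, two-sided 5%, d = 1.36 with SD 1, Normal data (10.5); Mann-Whitney test (10.1). All results are for a single comparison.

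**Step 1: reproduce the plan's figure.** The method is t-test power with the sample size multiplied by the Mann-Whitney asymptotic relative efficiency for Normal data, 3/π = 0.955.

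- Effective n per arm = 10 × 0.955 = 9.55
- Degrees of freedom = 2 × 9.55 − 2 = 17.1
- Noncentrality = 1.36 × √(9.55/2) = 2.97
- Critical t (17.1 df, two-sided 5%) = 2.109
- Power from the noncentral t = 0.79997, or 80.0%; d for 80% = 1.3601

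The plan's pair of figures is recovered. A plain t-test without the efficiency factor would give 82.0%, or 80% at d = 1.325, so the stated figure already includes the Mann-Whitney efficiency loss.

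**Step 2: the test itself at 10 v 10.** Under the null, U has mean 10 × 10/2 = 50 and SD √(10 × 10 × 21/12) = 13.23.

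- Exact: two-sided size is 4.33% if U ≤ 23 rejects and 5.24% if U ≤ 24 does. Only U ≤ 23 keeps 5%.
- Continuity-corrected: U = 24 gives (26 − 0.5)/13.23 = 1.93, below 1.96, and U = 23 gives (27 − 0.5)/13.23 = 2.00, above it. The rejection region is the same as for the exact test.
- Uncorrected: U = 24 gives 26/13.23 = 1.965, just above 1.96. This version rejects at U ≤ 24, so its true size is 5.24%.

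Simulated power at d = 1.36 (1,000,000 Normal replicates):

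| Version | True size | Power |
|---|---|---|
| Exact | 4.33% | 77.9% |
| Continuity-corrected | 4.33% | 77.9% |
| Uncorrected normal | 5.24% | 80.5% |

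The exact test at 10 v 10 reaches 80.2% at d = 1.40.

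**Step 3: losses after randomisation.** No rate is given in the documents, so 1 to 3 experimental subjects is an assumption, shown as a range. Control-arm losses are left at zero.

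| Assumed handling | Analysed | Exact power | Efficiency-adjusted t |
|---|---|---|---|
| 1 removed | 9 v 10 | 75.2% | 77.6% |
| 2 removed | 8 v 10 | 72.1% | 74.6% |
| 3 removed | 7 v 10 | 68.1% | 70.9% |
| 1 counted in arm 2 | 9 v 11 | 78.3% | 79.6% |
| 2 counted in arm 2 | 8 v 12 | 77.3% | 78.4% |

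In each of these five settings the exact, corrected and uncorrected tests reject at the same values of U and so have the same power. The arm 2 rows keep d at 1.36 and allow for no dilution of the effect.

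**The case against.** The strongest reply is that nothing was miscalculated. The method is standard, it suits the named test, and it returns d = 1.36 at 80% to the precision given. That stands. A reader might infer that the sponsor used a t-test figure and forgot the cost of the rank test; step 1 shows otherwise. The gap between 79.997% and 80% is rounding of d and no part of this point.

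Second, 10.1 does not fix the version of the test, and one version does pass 80%. It is therefore too strong to say that the planned test certainly has 78%. But the version that passes does so by exceeding the 5% level that 10.5 states. None of the three versions checked both keeps 5% and reaches 80% at d = 1.36.

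Third, the shortfall at full numbers is about 2 points, or 0.04 in d, in a pilot that says it has no preliminary data on its primary endpoint. Here d describes what 20 subjects can detect and is not a target drawn from evidence. That also stands, and it limits the severity.

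Fourth, the removals are contingent. A reader might take 72% or 68% as the power the trial will have. The documents do not support that: they give no mobilisation-failure or withdrawal rate, they are silent on replacement, and 5.6 leaves open a transfer to arm 2 that costs less power.

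**Conclusion.** The statement in 10.5 should be corrected, as a minor point. At least 80% holds only as a large-sample approximation with 10 v 10 analysed. With a test that keeps the stated two-sided 5% level, power for one comparison is about 78% at d = 1.36, and 80% needs d of about 1.40.

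The lack of any allowance for losses matters more than the 2 points. Once one experimental subject is removed or counted in arm 2, power is below 80% under every version of the test and under the plan's own method. With 8 v 10, the chance of missing a true d = 1.36 is about 28% (100 − 72.1) instead of 20%.

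The conclusion rests on Normal data with equal SDs, as 10.5 assumes, and on assumed numbers of losses in step 3. It does not show that the trial is too small for its exploratory purpose.

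**What to change.** 1. In 10.5, replace the bound with: *about 78% power at d = 1.36 (80% at d = 1.40) for a single two-sided exact Mann-Whitney comparison with 10 evaluable subjects per arm.*
2. In 10.1, name the exact Mann-Whitney test.
3. In 10.5, add power under an assumed range of losses after randomisation, labelled as assumed: about 75%, 72% and 68% with 1, 2 or 3 experimental subjects removed, and about 78% and 77% if 1 or 2 are counted in arm 2, before any dilution.
4. Reconcile 5.1.6 and 5.6 on how subjects below the day 1 collection threshold are analysed, since this decides which of those figures applies. State also whether randomised subjects who are lost will be replaced.

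Items 1 to 3 cost wording only and make the stated power slightly less favourable. Item 4 needs a decision by the sponsor; its analysis part requires no new data collection.
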